10.0 Data and Specimen Banking

N/A

11.0 Data Analysis/Management

Describe the data analysis plan, including any statistical procedures.

Given the pilot nature of the R21 study, data analysis will be largely descriptive and exploratory. We will focus on parameter estimates instead of formal hypothesis testing. The feasibility and acceptability of the research protocol as outlined above is the main outcome of interest, as is now recommended for pilot studies, rather than effect size estimates.¹⁰⁹

Study aim 1: To test the feasibility and acceptability of the intervention

Feasibility will be assessed by (a) demand through inquiry and enrollment rates and (b) practicality and participation through attrition rates and adherence with intervention (attendance, percentage of days wearing and syncing Garmin, participation in Facebook group) and study procedures (screening, follow-up batteries, accelerometry).

Acceptability will be assessed through participant ratings and qualitative interviews.

Fidelity of the social media/text component will be evaluated following a procedure for prior mHealth intervention pilots conducted by the study team including tracking facilitator posts, participant views, likes, and posts. We will summarize the measures listed above using means, medians, and standard deviations for continuous variables and proportions for categorical variables and then conduct bivariate analyses. Non-parametric tests will be used on non-normally distributed continuous variables, and Fisher's exact test on sparse categorical variables. The proportions that reflect acceptability and feasibility will be assessed using 95% exact (Clopper-Pearson) confidence intervals

Exploratory Aim: To explore the effects of the intervention on PA

We will compare within-subject pre to post activity using accelerometer data (step count; sedentary, light and MVPA; sleep duration), MVPA as an exploratory outcome. We will examine gender as an effect modifier given that differences in PA are seen between boys and girls from an early age and differential effects of previous PA interventions by gender have been noted.(111) We will also look at associations of the measures from Aim 1 with PA outcomes. Pre- and post-intervention outcomes will be compared using t-

tests, paired t-tests, chi-square and when appropriate, Fisher's exact test. We will account for within-subject correlation due to repeated measures. Due to the pilot nature of the intervention, we emphasize the analyses will be primarily descriptive; confirmatory analysis will await future studies.

11.1 Provide a power analysis.

We anticipate needing to screen up to 45 children for low PA to ensure enrollment of 30 eligible families, but will screen more if needed. Treatment groups will begin on a rolling basis as soon as 6-8 eligible families have enrolled.

11.2 Describe any procedures that will be used for quality control of collected data.

N/A

12.0 Confidentiality

12.1 Describe the steps that will be taken to secure the data or specimens (e.g., training, authorization of access, password protection, encryption, physical controls, certificates of confidentiality, and separation of identifiers and data) during storage, use, and transmission.

We will take the following steps to ensure data will be secure during storage, use, and transmission: proper and consistent training of staff members, limit authorization of access to study team members, password protect the electronic data files, physically lock forms with identifiable information in a locked cabinet in staff offices, and ensure separation of identifiers and PHI data.

12.2 Describe how data and specimens will be managed study-wide

Staff will be informed of the need for confidentiality as information to be obtained will contain PHI (e.g. name, DOB, contact information, basic demographic info). Forms with identifiable names will be kept in a locked cabinet room in staff offices at SCRI. The electronic data files will not have any personally identifying names in the file, and will be kept on a secure HIPAA compliant server hosted by Children's for a minimum of 6 years. Digitally audio recorded interviews will be deleted following transcription and will not be kept on file. No names or addresses will be reported in publications. Only the PI, research coordinator, and research administrator have keys to the offices and locked cabinets at SCRI.

13.0 Provisions to Monitor the Data to Ensure the Safety of Subjects

13.1 Describe:

Prior to implementing the study, the protocols, information sheet, recruitment materials and evaluation procedures will be reviewed by Seattle Children's Institutional Review

Board. Any adverse events will be recorded and reviewed by the PIs ([name], [name]) and their study team. Any adverse event and the actions taken will be reported to the IRB at Seattle Children's Research Institute.

A two-person DSMB will be established for the proposed study who will advise the study investigators. The DSMB is comprised of (1) a pediatrician and NIH-funded investigator studying early childhood development ([name]), and (2) a psychiatrist and specialist in child and adolescent and mental health including ADHD, [name], Professor of Psychiatry & Behavioral Sciences at the University of Washington. Neither of the DSMB members are investigators or key personnel of the proposed research study, but all have expertise for essential components of the intervention.

The primary responsibilities of the DSMB will be to (1) periodically review and evaluate the accumulated study data for participant safety, study conduct and progress, and (2) make recommendations to the PI and co-investigators concerning the continuation, modification, or termination of this study. The PI and co-investigators will report any serious unexpected adverse event (whether associated with the intervention or not) to the DSMB, IRBs, and NIH within 48 hours by telephone and within 5-working days in writing. The DSMB and IRBs will also determine whether the adverse event is causally related, probably related, possibly related, or unrelated to the intervention. A serious unexpected adverse event is provisionally defined as any of the following:

- a) death
- b) any acute life-threatening event, including any serious physical activity-related injuries
- c) any event requiring hospitalization or emergency department care
- d) any other event that warrants a designation of a "serious" event in the PI's, Co-Is', or DSMB's judgment, including threats to safety or "near-miss" injury events that could have led to items a-c above

All other adverse events will be filed annually with the DSMB, the IRBs, and the NIH. Routine monitoring for adverse events will be performed by the study staff and coordinators, the PIs, and co-investigators. Since there are no investigational drugs or devices, there will be no routine post-study follow-up of participants.

Should a Caregiver or child enrolled in the study report concerning information related to suicidal ideation or safety in the course of their participation, [name] will meet with the family individually to further assess concerns, engage in safety planning as needed, and connect the participant with mental healthcare or emergency services. Regarding medical symptoms related to exercise, we will contact the participant's family and refer the child or parent for the appropriate medical attention with the family's primary care provider.

14.0 Withdrawal of Subjects

14.1 *Describe anticipated circumstances under which subjects will be withdrawn from the research without their consent.*

We do not anticipate conditions where subjects will be withdrawn from the research without their consent.

14.2 *Describe any procedures for orderly termination.* N/A

14.3 *Describe procedures that will be followed when subjects withdraw from the research, including partial withdrawal from procedures with continued data collection.*

Should subjects withdraw from the research, we will keep their data (unless requested otherwise from subject) for later analyses. Like all other data to be analyzed, subjects who withdraw will have their data de-identified and kept on HIPAA compliant servers. As much as possible, we will remove content posted by the participant from the Facebook group and direct the participant to delete the Garmin app.

15.0 Risks to Subjects

15.1 *List the reasonably foreseeable risks, discomforts, hazards, or inconveniences to the subjects related to the subjects' participation in the research. Include as may be useful for the IRB's consideration, describe the probability, magnitude, duration, and reversibility of the risks. Consider physical, psychological, social, legal, and economic risks.*

There are no drugs or devices used in this study. This is a minimal risk study that has no potential serious harms or risks related to participating in this study. Study procedures may include possible participant discomfort as discussing personal experiences and opinions may become emotional for participants. To avoid or mitigate any psychological risks, research staff will be trained to provide appropriate support and help participants calm in the even that s/he becomes emotional. Participants may also be offered a break and reminded that they can take as much time as needed. Subjects may feel some discomfort wearing the Garmin wrist activity tracker or the Actigraph hip-worn activity meter but these devices are designed for daily use and have been used by our research group (and others here at Seattle Children's) without major incident. The Facebook page will be monitored each weekday by study staff in order to ensure that inappropriate language or behavior between study participants is identified.

15.2 *If applicable, indicate which procedures may have risks to the subjects that are currently unforeseeable.*

N/A

15.3 *If applicable, indicate which procedures may have risks to an embryo or fetus should the subject be or become pregnant.*

N/A

15.4 *If applicable, describe risks to others who are not subjects.*

For others who are not subjects (e.g. other family members not participating in the study), there may be risk of emotional or social discomfort should participant discuss challenges related to group participation (e.g., discussion of ADHD-related difficulties) or use of program skills at home

(implementation of consequences, rewards), or inconvenience of accommodating lifestyle changes to increase PA caused by the program.

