8.0 Study Endpoints

8.1 *Describe the primary and secondary study endpoints.*

The study endpoint is the completion of all subjects' participation in the study intervention and completion of all data collection and analysis.

8.2 *Describe any primary or secondary safety endpoints.*

N/A

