We will create a private (invitation only) Facebook group for each LEAP intervention group to provide encouraging advice and messages to promote PA, announce weekly individual and group badges/awards (e.g., most improved, most steps, most active minutes, most Facebook posts, etc.), and to provide a forum for participants to discuss PA and use of the Garmin devices. A group facilitator profile will be created with which research assistants can post to the group page, interact with participants, and screen content posted by members daily to remove it if inappropriate. The facilitator will make about 5 posts per week providing encouragement, reminders and study procedures, and opportunities to troubleshoot and answer questions. We have included a manual with information on planned posts. Participants will earn digital badges for meeting their weekly activity goals, as well as for social interactions (e.g. "liking" other's posts) or making improvement toward goals to ensure that all participants receive positive feedback. We will begin the first 4 weeks with badges awarded to individuals only (e.g. most improved individual, most steps (from baseline) for an individual, etc.). Starting in week 5, we will award additional badges contingent on the entire intervention group meeting pre-specified criteria (e.g. 250,000 steps attained). This "all for one and one for all" approach is designed to foster encouragement and cooperation among the participants to promote PA and to keep participants engaged. Participants will be encouraged but not required to post in the group and to encourage their fellow participants. Participants will also receive standardized weekly text messages (using a free service) reminding them to wear/sync their Garmin and increase PA in their family routines. The facilitator and investigators will build upon the operations manual used in our teen ADHD pilot study to add practical information and troubleshooting tips for the purposes of training and guiding others to fulfill the role as independently as possible. Facilitator will track time spent each week as an indicator of implementation burden.

Questionnaires/Measures – listed in Table 2; completed by teachers, caregivers, child participants, or therapists. Of the measures listed below, we will submit the HBD for IRB approval prior to administration.

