Assessments and study groups will be conducted at Seattle Children's Hospital. The co-PI ([name]) and several of the Co-Is ([name], [name]) have offices there. There are private treatment and group rooms available for the study.
- *Describe the availability of medical or psychological resources that subjects might need as a result of an anticipated consequences of the human research.*

Physical activity is taking place in the participants' own homes and neighborhoods. We will refer patients to consult regarding fitness-related concerns or injuries with their primary care doctor. The need for additional psychological resources will be assessed by the Co-PIs or Co-Is. Emergency services are available at Seattle Children's. We will facilitate referrals for individual mental health treatment within Outpatient Psychiatry or in the community if needed.

- *Describe your process to ensure that all persons assisting with the research are adequately informed about the protocol, the research procedures, and their duties and functions.*

Upon hiring, the co-PIs will provide training in the study protocol to all hired research assistants or other personnel working on the study. Job descriptions will be provided prior to hiring. The co-PIs will supervise all personnel on the study.

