27.0 Compensation for Research-Related Injury

This research does not involve more than Minimal Risk to subjects and research is unlikely to result in injury.

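### Adverse-event monitoring is promised but no way of asking families about injuries is defined, and the risk statement and the frequency of Facebook checks differ between sections

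*Combined protocol and SAP*

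**What the plan says.** **Harms monitoring.** Section 13.1 says that adverse events will be recorded and reviewed by the PIs and that study staff, coordinators and investigators will monitor for them routinely. Serious unexpected events are reported quickly to the DSMB, the IRBs and NIH; all others are filed annually. A two-person DSMB periodically reviews the accumulated data for safety. The provisional definition of a serious unexpected event includes "any acute life-threatening event, including any serious physical activity-related injuries", emergency department care or hospitalization, and near-miss injuries.

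**Safety endpoints and measures.** The prompt in Section 8.2, "Describe any primary or secondary safety endpoints", is answered N/A. Table 2 (Section 9.2) has no row for adverse events or injuries at any visit. Section 11.0 describes no harms summary.

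**Risk statement.** Section 15.1 states "This is a minimal risk study that has no potential serious harms or risks related to participating in this study". The risks to subjects that it then names are emotional discomfort and discomfort from wearing the devices. The same sentence about serious harms recurs in Section 26.1. Section 21.2 says "We will refer patients to consult regarding fitness-related concerns or injuries with their primary care doctor", and Section 27.0 says "research is unlikely to result in injury". Section 17.0 judges that extra opportunities for activity are unlikely to raise children's risk significantly.

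**Facebook group.** Section 15.1 says "The Facebook page will be monitored each weekday by study staff". Section 9.2 says that research assistants will "screen content posted by members daily to remove it if inappropriate", and Section 24.0 repeats this.

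**The concern.** The purpose of the intervention is to make children more active, and Section 21.2 places that activity in homes and neighborhoods, out of sight of staff. Activity-related injury is the obvious physical harm to track. Yet the plan does not say how staff will find out about such events, when they will ask, or how many children will have been asked.

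A pilot's harms record is useful only if its denominator is known. Without a defined question, a report of no injuries could mean that none happened or that some were never recorded. The DSMB's review and any later, larger study would inherit that ambiguity. The gap is not confined to minor events: an emergency department visit meets the protocol's own definition of a serious event, but it can be reported only once staff learn of it.

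The other two matters are about consistency. The section meant to list foreseeable risks, whose prompt asks for physical risks to be considered, leaves out a risk that other sections make provision for. And the safeguard for the Facebook group is stated at two different frequencies.

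**Working it through.** The documents give no figure on harms, so there is none to reproduce. The check is a comparison of sections, plus arithmetic for scale.

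**1. What is defined for capturing harms**

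| Element | Where looked for | Found |
|---|---|---|
| Commitment to record, monitor and review | 13.1 | Yes |
| Reporting routes and DSMB | 13.1 | Yes |
| Question or form for families | 9.2, Table 2, 13.1 | Not stated |
| Timing of asking | 9.2, Table 2, 13.1 | Not stated |
| Safety endpoint | 8.2 | N/A |
| Summary of harms, with denominator | 11.0 | Not stated |

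Oversight is planned. The step that would supply it with data is not specified.

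**2. What a zero count would mean**

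Input: n = 30 families to be enrolled (Sections 11.1 and 25.0), one child each.

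- All 30 asked, no events: the exact two-sided 95% upper limit is 1 − 0.025^(1/30) = 11.6%. The one-sided limit is 1 − 0.05^(1/30) = 9.5%.
- Suppose only half of affected children are recorded (an assumption; the documents give no capture rate). The limit then applies to half the true risk, so the true risk could be as high as 11.57% / 0.5 = 23.1%.

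The chance of recording at least one affected child is 1 − (1 − p)^30 with full capture and 1 − (1 − p/2)^30 with half capture. The per-child risks p are assumed:

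| p | Full capture | Half capture |
|---|---|---|
| 1% | 26% | 14% |
| 2% | 45% | 26% |
| 5% | 79% | 53% |
| 10% | 96% | 79% |

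These figures show no error in the plan. They show that a sample of 30 says little about harms even with complete ascertainment, and less when the capture rate is unknown.

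**3. Section 15.1 against the other sections**

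- 15.1: no potential serious harm; activity injury not listed.
- 13.1: serious activity injuries and near-misses are reportable if they occur, and there is a plan for medical symptoms related to exercise.
- 21.2: a referral route for injuries.
- 27.0: injury unlikely, which is weaker than absent.
- 17.0: added activity considered and judged unlikely to raise risk significantly.

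Sections 13.1, 17.0, 21.2 and 27.0 are compatible with one another: the risk is small, not zero, and handled if it arises. Section 15.1 is the outlier because its wording is absolute.

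**4. Facebook checks**

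Sections 9.2 and 24.0 say daily; Section 15.1 says weekdays. Under the weekday statement, 7 − 5 = 2 days each week have no stated check. Both cannot describe the same procedure.

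**The case against.** The strongest reply is that the safety plan is in Section 13.1 and is substantial for a single-arm behavioral pilot: recording, routine staff monitoring, expedited reporting and a DSMB. Staff also meet or contact families weekly through group sessions and coaching, so there are many occasions to hear of an injury. This stands, and it rules out two stronger readings that a reader might infer: that events are captured only if families volunteer them, and that no systematic harms data are collected. The documents support neither. They show monitoring that is promised but not specified.

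A reader might also infer from Table 2 that no assessment asks about injuries. The items of the Health Behaviors Survey, given at baseline, week 5 and week 9, are not in the documents, so the statement holds only for what Table 2 lists. Nor can one conclude that families are not told of the risk: the consent pages are not available for review, and Section 15.1 answers an IRB prompt rather than addressing families.

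On the risk wording, the injuries in 13.1 appear in a provisional reporting definition of unexpected events. Making an event reportable does not predict it, and Section 17.0 does address added activity. This stands as a defense of the minimal-risk classification. It does not justify saying that no serious harm is possible, or leaving injury out of the list of foreseeable risks.

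Finally, a formal safety endpoint may seem excessive in a descriptive study of 30 families. That is a fair limit on ambition, and a simple count with its denominator would be enough.

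**Conclusion.** The concern holds in limited form. Harms oversight is planned, but the protocol defines no method or schedule for asking families, no harms item in Table 2 and no safety summary. Non-serious injuries and emergency visits could be under-recorded, and a zero count would be hard to interpret: an upper limit of 11.6% if all 30 children were asked, and 23.1% under an assumed half capture. The actual capture rate and injury risk are unknown, so the extent of any under-recording cannot be stated.

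The wording of Section 15.1 is in tension with 13.1, 21.2 and 27.0. A reader might take this as a strict contradiction or as a sign that the study is unsafe or misclassified; with Section 17.0 in view, the documents support neither. The daily and weekday statements on Facebook checks do conflict. None of this affects the feasibility, acceptability or activity estimates. It is a cheap improvement that should be made, not a flaw that undermines the study.

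**What to change.** 1. Add one standard question to the existing digital parent battery at weeks 5 and 9, asking about injuries and emergency or hospital visits since the last assessment. In Section 8.2 or 11.0, state that the number and proportion of children with an event, out of those whose parent was asked, will be reported with the exact (Clopper-Pearson) interval already planned for the feasibility proportions. If the Health Behaviors Survey already contains such an item, cite it in Table 2 instead.
2. Reword Section 15.1, and the identical sentence in 26.1, to be consistent with Sections 13.1, 17.0, 21.2 and 27.0. Name activity-related injury among the foreseeable risks and keep the minimal-risk classification.
3. Reconcile the frequency of Facebook content checks across Sections 9.2, 15.1 and 24.0, so that one statement applies throughout.

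The cost is one extra question at two time points, a few lines of protocol text and a slightly less favorable risk statement. No change to sample size, visits or the main analyses is needed.
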